## **Appendix C: Criteria for the Assessment of Severity of Illness in Patients with COVID-19**

### SARS-CoV-2 infection without symptoms

- Positive testing by standard reverse transcription polymerase chain reaction (RT-PCR) assay or equivalent test
- No symptoms

### Mild COVID-19

- Positive testing by standard RT-PCR assay or equivalent test
- Symptoms of mild illness that could include fever, cough, sore throat, malaise, headache, muscle pain, gastrointestinal symptoms
- No clinical signs indicative of Moderate, Severe, or Critical Severity

### Moderate COVID-19

- Positive testing by standard RT-PCR assay or equivalent testing
- Symptoms of moderate illness with COVID-19, which could include any symptom of mild illness or shortness of breath with exertion
- Clinical signs suggestive of moderate illness with COVID-19, such as RR  $\geq$  20, HR  $\geq$  90, or requires  $\leq$ 2L oxygen by nasal cannula in order maintain SaO2  $\geq$ 93%
- No clinical signs indicative of Severe or Critical Illness Severity

### Severe COVID-19

- Positive testing by standard RT-PCR assay or an equivalent test
- Symptoms suggestive of severe systemic illness with COVID-19, which could include any symptom of moderate illness or shortness of breath at rest, or respiratory distress
- Clinical signs indicative of severe systemic illness with COVID-19, such as RR  $\geq$  30, HR  $\geq$  125, requires  $>$  2L oxygen by nasal cannula in order maintain SaO2  $\geq$ 93%, or PaO2/FiO2  $<$ 300
- No criteria for Critical Severity

### Critical COVID-19

- Positive testing by standard RT-PCR assay or equivalent test
- Evidence of critical illness, defined by at least one of the following:
  - Respiratory failure defined based on resource utilization requiring at least one of the following:

- Endotracheal intubation and mechanical ventilation, oxygen delivered by high-flow nasal cannula (heated, humidified, oxygen delivered via reinforced nasal cannula at flow rates >20 L/min with fraction of delivered oxygen  $\geq 0.5$ ), noninvasive positive pressure ventilation, ECMO, or clinical diagnosis of respiratory failure (ie, clinical need for one of the preceding therapies, but preceding therapies not able to be administered in setting of resource limitation)
  - Shock (defined by SBP < 90 mm Hg, or Diastolic BP < 60 mm Hg or requiring vasopressors)
  - Multi-organ dysfunction/failure
-

1 INTRODUCTION

This statistical analysis plan (SAP) is consistent with the statistical methods section of the final study protocol (Version 4.0, dated 28 July 2020) and includes additional details of efficacy and safety summaries to be included in the clinical study report (CSR).

2 STUDY OBJECTIVES

2.1 Efficacy

2.1.1 Primary Objective

- To assess the effectiveness of NasoVAX in preventing clinical worsening in patients with early COVID-19

2.1.2 Secondary Objectives

- To assess the effects of NasoVAX on the severity of COVID-19, as indicated by changes in resting peripheral oxygen pulse saturation (SpO₂) and resting pulse rate
- To assess the effects of NasoVAX on rates hospital admission, oxygen supplementation and mechanical ventilation

2.2 Safety

- To assess the safety and tolerability of NasoVAX in patients with early COVID-19

3 STUDY ENDPOINTS

3.1 Primary Efficacy Endpoint

The primary endpoint is the proportion of patients with clinical worsening, defined as a 4.0% decrease from Baseline in resting SpO₂ by mobile pulse oximetry on two consecutive measurements during home follow-up, or hospitalization.

Baseline is defined as data collected closest to randomization prior to any study drug dosing. For resting SpO₂ and resting pulse rate, Baseline is defined as the average of the two measurements at Screening.

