### **3 STUDY ENDPOINTS**

#### **3.1 Primary Efficacy Endpoint**

The primary endpoint is the proportion of patients with clinical worsening, defined as an absolute 4.0% decrease from Baseline in resting SpO2 on two consecutive measurements during home follow-up, or hospitalization.

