#### **8.2.5      *Additional Data Collection in Hospitalized Patients***

Additional data to be collected for patients hospitalized due to COVID-19 through Day 42 to include the following:

- Date and time of hospital admission and discharge
- If transferred to ICU, date and time of ICU admission and discharge
- Requirement for oxygen (yes/no), and if yes, method of oxygenation (mask/nasal prongs, non-invasive ventilation, or high-flow oxygen; intubation and mechanical ventilation
  - If required ventilation, start date and time of ventilation, method of ventilation including whether intubated (yes/no)
- Change in ambulatory status
- Death

It is anticipated that most of this information will be obtained from the medical record. When necessary, a family member, designated legal representative or caregiver, as permitted by informed consent, will be contacted if the patient has expired or is too ill or otherwise unable to provide this information.

The rate (liters/min) of oxygen administered is to be captured as a concomitant medication. If, in the Investigator's opinion, a patient required a higher level of oxygenation, but did not receive due to resource availability, this should be documented.

---

Furthermore, if, in the Investigator's opinion, the patient required a higher level of care (ie, admittance to the ICU) but did not receive due to resource availability, this should be documented.

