### **10.3.2 Analysis of Efficacy**

For the primary analysis, the proportion of patients with clinical worsening, defined as a 4.0% decrease from Baseline in resting SpO2 on two successive measurements during home follow-up or hospitalization, will be compared between NasoVAX and placebo groups using the Cochran-Mantel-Haenszel test, while considering the stratification of age groups and risk factors, at a one-sided significance level of 0.025. The same approach will be applied for secondary endpoints that are categorical in nature. Sensitivity analyses will be performed to assess the effect of site on the response to study drug. Linear and logistic regression will be employed to examine the effects of Baseline factors, such as age, sex, medications, and medical co-morbidities on response.

Changes from Baseline in Severity of COVID-19, assessed by average decrease in resting SpO2, average increase in resting pulse rate by outpatient pulse oximetry and COVID-19 symptoms (eDiary) during home follow-up, will be analyzed using a mixed model for repeated measures. The model will include the fixed effects of treatment, week, and treatment-by-visit interaction as well as the continuous, covariate of Baseline level. The model will employ an unstructured within patient covariance matrix and a restricted maximum likelihood estimation method.

A Kaplan-Meier method will be applied to compare changes between treatment groups in resting SpO2 over time.

For the purpose of study efficacy endpoints, resting SpO2 and resting pulse rate will be assessed on observed data only; if data is missing, it will not be imputed.

No multiplicity adjustments will be made for secondary endpoints.

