3.2 Secondary Efficacy Endpoints

Secondary efficacy endpoints are:

1. Maximal severity of COVID-19 after treatment, as assessed by the following:
 - average decrease in resting SpO₂ from Baseline resting SpO₂ at Screening during the 14 days of home follow-up or hospitalization
 - average increase in resting pulse rate from Baseline resting pulse rate at Screening during the 14 days of home follow-up or hospitalization
 - proportion of patients requiring hospitalization through Day 42 according to maximal level of oxygen supplementation:
 - No oxygen supplementation
 - Oxygen supplementation with nasal cannulae
 - Oxygen supplementation with high flow device or non-invasive ventilation
 - Mechanical ventilation
2. All-cause mortality through Day 42

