9.9 Analysis of Efficacy Data

Efficacy analyses will be conducted using the mITT and PP Populations with the primary conclusions drawn from the mITT Population. Placebo will be the collective (pooled) across cohorts.

Descriptive statistics will be used to evaluate differences between Baseline and post-Baseline efficacy endpoints. The study is considered exploratory, and inferential statistics will be employed as appropriate.

For the purpose of study efficacy endpoints, resting SpO₂ and resting pulse rate will be assessed on observed data only; if data is missing, it will not be imputed.

The p-values from significance tests will be obtained at a one-sided significance level of 0.025.

No multiplicity adjustments will be made for the efficacy endpoints.

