9.9.3 Analysis of Time to Event Data Endpoints

Time to event data endpoints – the primary endpoint of the first 4.0% decrease or greater from Baseline in resting SpO₂ on two consecutive measurements during the 14 days of home follow-

up, or hospitalization; the secondary endpoints of the first incidence of resting pulse rate ≥ 125 beats per minute during the 14 days of home follow-up, or hospitalization; and all-cause mortality through Day 42 – will be analyzed by the Kaplan-Meier method. The summary statistics will be tabulated by treatment arms over visits and will include number of patients without event, number patients censored, 25th, 50th, and 75th percentiles with 95% CIs, the event rates across all visits with 95% CIs. Kaplan-Meier estimates are calculated with the PROC LIFETEST procedure in SAS. The CIs of the event rates will be calculated via log-log transformation method (default option CONFTYPE=LOGLOG in SAS) based on standard errors computed using the Greenwood's formula. Time to event data comparisons will be made by treatment group and may include comparisons for cohort or stratification factors (ages 35-64 years vs. ages 65 years and above, one or more risk factors present vs. no risk factors present). The summary statistics may also have the p-values from log-rank test to compare changes in events between NasoVAX cohorts and pooled placebo and overall NasoVAX and pooled placebo groups. The log-rank test stratified by age groups and risk factors will also be performed. The Kaplan-Meier curves will also be plotted for each NasoVAX cohort and pooled placebo groups.

Non-informative censoring is assumed, as censored patients the same probability of experiencing an event as patients that remain in the study. Patients who do not meet the event or loss to follow-up before the study-end are censored at the last day during the 14 days of home follow-up or hospitalization in resting SpO₂ and resting pulse or at Day 42 for all-cause mortality.

9.9.4 *Analysis for Covariates*

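### The primary clinical-worsening composite omits death, so a death outside hospital without two qualifying SpO2 readings counts as no worsening

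*SAP*

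**What the plan says.** Protocol 3.1 and SAP 3.1 define clinical worsening by two routes. The first is a 4.0% fall in resting SpO2 from Baseline, confirmed at a second consecutive home reading. The second is admission to hospital. The SAP wording is "by mobile pulse oximetry on two consecutive measurements during home follow-up, or hospitalization" and the protocol wording is "on two consecutive measurements during home follow-up, or hospitalization". The analysis section, Protocol 10.3.2, repeats the pair: "on two successive measurements during home follow-up or hospitalization, will be compared between NasoVAX and placebo groups". SAP 9.9.1 and 9.9.3 use the same two routes. None of these statements mentions death.

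Death appears as a separate secondary endpoint in SAP 3.2, "All-cause mortality through Day 42", with its own Kaplan-Meier analysis in SAP 9.9.3.

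Three further rules decide how a death is handled in the primary analysis:

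- **Missing data.** SAP 9.9 says that SpO2 and pulse rate "will be assessed on observed data only; if data is missing, it will not be imputed". SAP 9.9.6 allows, but does not require, sensitivity analyses that impute data missing because of death or hospitalization by LOCF or multiple imputation.
- **Censoring.** In SAP 9.9.3, patients who do not meet the event are censored within the 14-day home period. The section adds: "Non-informative censoring is assumed".
- **Analysis set.** The mITT set (Protocol 10.2, SAP 9.5) requires a dose, a Baseline value and at least one post-Baseline SpO2 reading.

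**The concern.** The primary objective is to prevent clinical worsening, and death is its extreme form. After Day 1 patients are at home and SpO2 is self-measured, seated and on room air. A patient who deteriorates quickly or becomes too ill to measure, and who dies before admission, need not produce two consecutive low readings. Home SpO2 monitoring stops at Day 14 while telephone follow-up runs to Day 28. In Days 15 to 28, hospitalization is the only route left for a patient with no earlier event.

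If such deaths differ between arms, the primary comparison is biased in favour of the arm that has more of them. The mortality endpoint would show the deaths but would not change the primary result.

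**Working it through.** The documents state no power, effect size or event rate (Protocol 10.1, SAP 9.4), so there is no plan figure to reproduce. The check has two parts.

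**Part 1: how each kind of death is scored under the written rules**

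| Patient (dosed, with Baseline) | Primary proportion | Kaplan-Meier of the primary event |
|---|---|---|
| Admitted, then dies | Event, through hospitalization | Event |
| Two consecutive qualifying readings, then dies at home | Event, through SpO2 | Event |
| At least one post-Baseline reading, neither route met, dies outside hospital | Non-event, in the denominator | Censored, assumed non-informative |
| Dies before any post-Baseline reading | Not in mITT | Not in mITT |

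The last two rows are the gap. The plan does not state the third row in words; it follows from the definition together with the observed-data rule. The optional LOCF analysis does not repair it, because carrying forward a last reading above the threshold still gives no event. Non-informative censoring cannot hold for a death, since the patient is no longer at risk of either route.

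**Part 2: scale**

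Arm size, from the cohort sizes in SAP Table 1: 10 + 14 + 24 = 48, and 2 × 48 = 96.

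Effect of one reclassified patient on an arm: 1/48 = 2.1 points. SAP 9.9.1 also compares each NasoVAX cohort with pooled placebo. There one patient is 1/10 = 10.0, 1/14 = 7.1 or 1/24 = 4.2 points of the NasoVAX cohort.

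Chance of at least one unscored death among 96 patients, 1 − (1 − q)^96, where q is the out-of-hospital death rate. All values of q are assumptions.

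| Assumed q | Expected deaths (96q) | Chance of at least one |
|---|---|---|
| 0.05% | 0.05 | 5% |
| 0.2% | 0.19 | 17% |
| 0.5% | 0.48 | 38% |
| 1% | 0.96 | 62% |
| 2% | 1.92 | 86% |

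Effect on the test, with assumed event counts and 48 per arm. One-sided Fisher exact p-values stand in for the stratified Cochran-Mantel-Haenszel (CMH) test, because counts by stratum are not available.

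| NasoVAX vs placebo events | Change | One-sided p |
|---|---|---|
| 3 vs 11 | as the plan would score | 0.020 |
| 4 vs 11 | one NasoVAX death counted | 0.045 |
| 3 vs 12 | one placebo death counted | 0.011 |
| 5 vs 7 | as the plan would score | 0.38 |
| 7 vs 7 | two NasoVAX deaths counted | 0.61 |

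In the first example one death moves the result across 0.025. In the last pair the estimate goes from 5/48 = 10.4% against 7/48 = 14.6% to 14.6% in both arms, but neither p-value is near 0.025.

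**The case against.** The case for leaving the endpoint alone is that the gap is narrow and the deaths are visible elsewhere.

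- Patients also measure SpO2 whenever symptoms worsen, not only twice a day.
- They are telephoned daily from Day 2 to Day 14. A family member or caregiver is contacted if they do not answer, and the call asks whether a clinic or hospital visit is needed (Protocol 8.2.3, Appendix A).
- Entry requires SpO2 of at least 96.0% on two readings. It excludes patients judged likely to be admitted within 24 to 48 hours.
- Deaths after admission are already events, mortality has its own endpoint, and the DMC is told of each death.
- The study is exploratory and was not sized for significance.

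All of this stands and lowers the expected number of unscored deaths. It does not give the remaining ones a correct score.

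A reader might also infer that the protocol expects patients to die for lack of access to care, from its instruction to document when "the patient required a higher level of care (ie, admittance to the ICU) but did not receive due to resource availability". That inference fails. The text is in Protocol 8.2.5, which covers patients already in hospital, and they are already primary events. It also asks for documentation if a shortage occurs; it does not predict one.

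**Conclusion.** The omission is explicit and consistent in both documents, and its scoring consequence follows from the plan's own rules. It affects only deaths outside hospital without two consecutive qualifying readings, and deaths before any post-Baseline reading. These are probably few. Each of the former, once counted, moves an arm of 48 by 2.1 points. Whether any occurs depends on a rate that the documents do not give: about a 5% to 86% chance of at least one over assumed rates of 0.05% to 2%. With assumed counts, one such death can change the one-sided 0.025 conclusion, but in other cases even two would not.

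The tempting stronger reading is that the primary result is already unreliable, or that the plan hides deaths. The documents support neither. Deaths are recorded, analysed as a secondary endpoint and reviewed by the DMC, and any bias requires such deaths to occur unequally between arms. This is something that should be fixed, not a defect that invalidates the trial.

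**What to change.** Make the change in both documents (Protocol 3.1, 10.2 and 10.3.2; SAP 3.1, 9.5, 9.9.1 and 9.9.3). Protocol 10.4 says the primary analysis stays as the protocol has it, so changing the SAP alone is not enough.

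1. Define clinical worsening as the SpO2 criterion, or hospitalization, or death from any cause.
2. State the time window. Day 28 is the last routine contact for patients not in hospital; a later window would need extra contact with them.
3. Count death as an event in the CMH analysis. In the Kaplan-Meier analysis count it on its date and never as censoring, and align the follow-up period with the chosen window.
4. Keep dosed patients who die before any post-Baseline SpO2 reading in the primary analysis set, as events.
5. Report the three components separately.

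The cost is a protocol amendment, a few phrases in the SAP and a small change to the endpoint derivation. Vital status is already documented at each contact (Protocol 8.2.6), so a window to Day 28 needs no new data collection. The downside is that the primary event rate may rise slightly and deaths unrelated to COVID-19 would count; separate reporting of the components makes both visible.

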3.2 Secondary Efficacy Endpoints

Secondary efficacy endpoints are:

1. Maximal severity of COVID-19 after treatment, as assessed by the following:
 - average decrease in resting SpO₂ from Baseline resting SpO₂ at Screening during the 14 days of home follow-up or hospitalization
 - average increase in resting pulse rate from Baseline resting pulse rate at Screening during the 14 days of home follow-up or hospitalization
 - proportion of patients requiring hospitalization through Day 42 according to maximal level of oxygen supplementation:
 - No oxygen supplementation
 - Oxygen supplementation with nasal cannulae
 - Oxygen supplementation with high flow device or non-invasive ventilation
 - Mechanical ventilation
2. All-cause mortality through Day 42

3.3 Safety Endpoints

Safety endpoints are:

- Incidence and severity of adverse events (AEs)
- Oral temperatures
- Use of antipyretics and bronchodilators
- Hospital length of stay, and intensive care unit (ICU) length of stay

4 STUDY DESIGN

4.1 General

This is an exploratory Phase 2 clinical study to evaluate the protective effects of NasoVAX in patients with early COVID-19. Approximately 96 ambulatory patients with COVID-19, with onset of symptoms (fever, cough, and/or shortness of breath) within 48 hours and a diagnosis within the prior 24 hours, will be enrolled in 3 successive cohorts defined by age and risk factors for severe COVID-19 (Exclusion Criterion 5 in the Protocol) ([Table 1](#)) (Cohort 1, ages 35-49 years and risk factors disallowed; Cohort 2, ages 35 and above and risk factors disallowed; and Cohort 3, ages 35 and above and risk factors allowed) of approximately 20, 28, and 48 patients,

respectively. The cohorts will be enrolled in ascending order, with Cohort 1 preceding Cohort 2, and Cohort 2 preceding Cohort 3).

Study conduct will be overseen by a Data Monitoring Committee (DMC), which will monitor the safety of study participants and review safety data real-time during the course of the study. If any of the Stopping Rules ([Section 5.1.2](#)) are met, enrollment and study drug treatment will be temporarily halted pending DMC review.

Once a cohort is fully enrolled, enrollment will be paused until all patients either complete 14 days of home assessments or they are determined to have been hospitalized. The DMC will then review the safety and tolerability data and make a recommendation regarding whether to progress to the next cohort. The DMC may unblind the data in conducting its assessments although treatment allocation will not be revealed to operational study personnel.

Upon signing informed consent, patients will undergo Screening assessments at the study center, as per the Schedule of Events ([Table 2](#)). Within each cohort, patients who are determined to be eligible will be randomized that same day (Day 1) in a 1:1 ratio to receive either NasoVAX or placebo with approximately 10 and 14 patients in Cohorts 1 and 2, respectively, receiving NasoVAX and 10 and 14 receiving placebo in Cohorts 1 and 2, respectively ([Table 1](#)). Approximately 24 patients will receive NasoVAX and 24 will receive placebo in Cohort 3. Randomization in Cohort 2 will be stratified by age groups of 35-64 years and 65 years and above. Randomization in Cohort 3 will be stratified by age groups (ages 35-64 years, ages 65 and above) and co-morbidity (one or more risk factors present, no risk factors present). Enrollment of patients ages 35-49 will not exceed approximately 30% of the randomized population of either treatment arm.

Table 1 Study Design

Cohort	Cohort Description	Number of Doses	NasoVAX Dose (vp)	Number of patients	
				NasoVAX	Placebo
1	Ages 35-49 years and risk factors disallowed	Single	1 x 10 ¹¹	10	10
2	Ages 35 and above and risk factors disallowed	Single	1 x 10 ¹¹	14	14
3	Ages 35 and above and risk factors allowed	Single	1 x 10 ¹¹	24	24
Group Total				48	48
Study Total				96	

Study drug will be administered as a single intranasal dose of 0.5 mL (0.25 mL each nostril) in the supine position after which patients must remain in the supine position for 30 minutes. Patients will be observed for at least 2 hours post intranasal administration. Patients who are randomized will be considered enrolled in the study.

No in-person visits are expected during the study after Day 1 unless a participant experiences a change in symptoms or AE that requires a visit for assessment.

Prior to discharge from the study center on Day 1, patients will be provided with:

- A fingertip pulse oximetry device that connects to a mobile device connecting to a tablet that will be supplied to the patient to measure resting SpO₂ and resting pulse rate remotely. Patients will be trained on the use of the device and tablet.
- A digital thermometer for measurement of oral temperature
- Instructions regarding how to take the above measurements and access and complete a web-based electronic diary (eDiary)

After discharge on Day 1, patients will return home for the duration of the study. Patients are to measure resting SpO₂, resting pulse rate, and oral temperature twice daily at 09:00 hours and 16:00 hours, with a 1-hour window around each time point, and at any time they experience worsening symptoms until Day 14 or hospitalization, whichever comes first. Patients are to record COVID-19-related symptoms daily during this same time period. Study center personnel will contact patients daily by telephone during this period to document the patient's clinical status, record concomitant medications and monitor for AEs.

After Day 14, study center personnel will contact patients via telephone approximately every 7±2 days for 14 additional days to determine if they were hospitalized and to follow AEs that were not resolved by Day 14. If the patient is hospitalized at any time, the dates and times of hospital admission/discharge, ICU admission/discharge, and ventilation requirement are to be recorded, as applicable. Patients who remain hospitalized at the end of 28 days will be followed through Day 42 or death, whichever is sooner.

